6.4. Analysis of safety

6.4.1. Analysis of safety planned in the protocol

The analysis for safety will be based on the Exposed set. All safety analyses may also be performed by age strata (50-59, 60-69 and \geq 70 YOA), if deemed necessary.

When appropriate, tabulations will be presented overall and by time of occurrence relative to last vaccination (e.g. using windows such as Days 1 to 7, Days 1 to 30 and more than 30 days post-vaccination).

The results for the analysis of safety will be tabulated as follows:

- The number and percentage of subjects with at least one local solicited AE, with at least one general solicited AE, and with any solicited AE during the 7-day follow-up period with exact 95% CIs after each vaccine dose and overall by vaccination group will be provided;
- The percentage of subjects reporting each individual solicited local and general AE during the solicited 7-day follow-up period will be tabulated with exact 95% CI;
- For all solicited adverse events, the same tabulation will be performed for grade 3 solicited AEs and for solicited general AEs with relationship to vaccination;
- Number of days with each individual solicited local and general AE during the solicited 7-day follow-up period;
- The proportion of subjects with at least one report of unsolicited AE (containing both serious and non-serious unsolicited AEs) classified by the MedDRA Primary System Organ Class (SOC) and Preferred Terms (PTs) and reported up to 30 days after each vaccination will be tabulated with exact 95% CI;
- The same tabulation will be performed for grade 3 unsolicited AEs and for unsolicited AEs with a relationship to vaccination reported up to 30 days after each vaccination with exact 95% CI. The proportion of AEs resulting in a medically attended visit will also be tabulated;
- Total number/percentages of doses (per dose and overall) followed by AEs will be tabulated:
- Number of subjects with pIMDs will be tabulated;
- SAEs, including fatalities and withdrawal due to AE(s) will be described in detail.

6.4.2. Additional considerations

- The following additional tables will be generated:
 - The percentage of subjects with at least one local AE (solicited and unsolicited), with at least one general AE (solicited and unsolicited) and with any AE (solicited and unsolicited) during the 7-day follow-up period will be tabulated with exact 95% CI after each vaccine dose and overall. The same computations

204487 (ZOSTER-059 PRI) Statistical Analysis Plan Amendment 3

- will be done for Grade 3 AEs, for any AEs considered related to vaccination and for any Grade 3 AEs considered related to vaccination.
- The percentage of subjects with at least one local solicited AE, with at least one general solicited AE and with any solicited AE will also be done for Grade 3 solicited AEs, for any solicited AEs considered related to vaccination and for any Grade 3 solicited AEs considered related to vaccination.
- The percentage of subjects reporting each individual solicited local AE during the solicited 7-day follow-up period will be tabulated by study vaccine with exact 95% CI.
- Summary of temperature value by half degree increment taken by different routes reported during the 7-day (Days 1-7) post-vaccination following each dose.
- For fever, the number and percentage of subjects reporting fever by half degree (°C) cumulative increments during the 7-day follow-up period (Day 1-7) will be tabulated for each group after each vaccine dose and overall. Similar tabulations will be performed for Grade 3 (> 39.0°C) causally related fever.
- List of suspected HZ cases identified during the study will be presented.
- The number and percentage of subjects starting a concomitant medication during the 30-day post-vaccination period by dose and overall will be presented.
- The duration of solicited local adverse events (in days), not limited to the 7-day post-vaccination period, following each dose and overall/dose. The same tabulations after Prevenar13 and HZ/su vaccinations.
- The duration of solicited general adverse events (in days), not limited to the 7day post-vaccination period, following each dose and overall/dose.
- Solicited local adverse events ongoing beyond the 7-day (Days 1-7) post-vaccination period, following each dose and overall/dose. The same tabulations after Prevenar13 and HZ/su vaccinations.
- Solicited general adverse events ongoing beyond the 7-day (Days 1-7) post-vaccination period, following each dose and overall/dose.
- Number and percentage of subjects with at least one report of a grade 3 non-serious unsolicited AE during the 30-day (Days 0-29) follow-up period after each vaccination classified according to the MedDRA Primary SOC and PTs will be tabulated, with exact 95% CI. The same will be generated for grade 3 non-serious unsolicited AE considered related to vaccination.
- Number and percentage of subjects with fatal SAEs, classified by MedDRA
 Primary SOC and PTs will be presented with exact 95% CI in two ways:
- With onset of fatal SAE during the period starting from first vaccination to 30 days post last vaccination dose, after 30 days post last vaccination dose to study end and from first vaccination to study end.

204487 (ZOSTER-059 PRI) Statistical Analysis Plan Amendment 3

- Who died during the period starting from first vaccination to 30 days post last vaccination dose, after 30 days post last vaccination dose to study end and entire study period.
- The listing of all subjects who died during the entire study period and their fatal SAEs in the Enrolled Set

6.4.2.1. Combined Solicited and Unsolicited Adverse Events

A summary of subjects with all combined solicited (regardless of their duration) and unsolicited adverse events will be provided. Solicited adverse events will be coded by MedDRA as per the following codes:

Solicited adverse event	Lower level term name	Corresponding Lower level term code
Pain	Injection site pain	10022086
Redness	Redness at injection site	10022098
Swelling	Swelling at injection site	10053425
Fatigue	Fatigue	10016256
Gastrointestinal symptoms	Gastrointestinal disorder	10017944
Headache	Headache	10019211
Myalgia	Myalgia	10028411
Shivering	Shivering	10040558
Temperature	Fever	10016558

For clintrial gov and EudraCT posting purposes, a summary of combined solicited and unsolicited non-serious adverse events will be produced by SOC and PTs and according to occurrence of each event

7. ANALYSIS INTERPRETATION

All co-primary objectives will be evaluated using a one-sided Type I error of 2.5% (as already justified by fixed sequential testing procedure, no alpha adjustment needed). The trial will be considered conclusive if all co-primary objectives criteria are met.

8. CONDUCT OF ANALYSES

8.1. Sequence of analyses

The analysis will be performed in the following steps:

• The final analysis on immunogenicity, reactogenicity and safety data will be performed when all data up to study end (i.e., phone contact at Month 14 for Co-Ad group and phone contact at Month 16 for Control group) will be available and cleaned. Individual data listings will also be provided.

An integrated clinical study report containing all data will be written and made available to the investigators following the final analysis.

204487 (ZOSTER-059 PRI) Statistical Analysis Plan Amendment 3

Table 5 Analysis and disclosure plan for the planned analysis

Description	Analysis ID	Disclosure Purpose (CTRS=public posting, CSR=clinical study report, internal)	Dry run review needed (Y/N)	Reference for TFL
Final analysis	E1_01	CTRS CSR	Y	All tables from Section 13 of the SAP Amendment 3 23NOV2020

8.2. Statistical considerations for interim analyses

Not applicable

9. CHANGES FROM PLANNED ANALYSES

- In Protocol Amendment 2 Final (30 Jan 2018), it was specified that a second analysis for immunogenicity of the ES would be performed only if, in any study group, the percentage of enrolled subjects with serological results excluded from the PPS for immunogenicity is 5% or more. At the request of Paul Ehrlich Institute, Germany (PEI), an analysis of the ES will be performed to complement the per-protocol analysis regardless of the percentage of enrolled subjects excluded from the PPS for immunogenicity.
- Updated LLOQ values (i.e. assay cut-off values) for the pneumococcal serotypes are provided in this version of SAP (section 12.1.2). The cut-off values presented in this SAP will be used to determine seropositivity rather than those presented in Protocol Amendment 2 Final (30 Jan 2018). Analysis of immunogenicity section has been updated accordingly.
- Additional tables on presentation of grade 3 non-serious unsolicited adverse events and fatal SAEs has been added based on CBER request.
- The sequence of analysis was updated from SAP amendment 1 to accommodate a delay in the availability of immunogenicity results. The active phase analysis has been removed as a request for a CTRS posting extension has been submitted to NIH; complete CTRS posting will be done at Last Subject Last Visit (LSLV) + 12 months rather than Primary Completion Date (PCD) +12 months as previously planned
- Two new cohorts Enrolled Set and Randomized Set has been defined as required for web disclosure and SAE tables presentation.
- Analysis of demography section has been updated to add consort table and summary of important protocol deviations.

204487 (ZOSTER-059 PRI) Statistical Analysis Plan Amendment 3

10. NON-STANDARD DATA DERIVATION RULES AND STATISTICAL METHODS

10.1. Statistical Method

10.1.1. Safety

For the listing of suspected HZ episode, following list of PT CODE has to be considered:-

PT_CODE	PT_NAME
10076667	Disseminated varicella zoster vaccine virus infection
10084396	Disseminated varicella zoster virus infection
10072210	Genital herpes zoster
10019974	Herpes zoster
10074297	Herpes zoster cutaneous disseminated
10061208	Herpes zoster infection neurological
10074259	Herpes zoster meningitis
10074248	Herpes zoster meningoencephalitis
10074251	Herpes zoster meningomyelitis
10079327	Herpes zoster meningoradiculitis
10074253	Herpes zoster necrotising retinopathy
10063491	Herpes zoster oticus
10074245	Herpes zoster pharyngitis
10080516	Herpes zoster reactivation
10030865	Ophthalmic herpes zoster
10074241	Varicella zoster gastritis
10074243	Varicella zoster oesophagitis
10074254	Varicella zoster pneumonia
10074298	Varicella zoster sepsis
10075611	Varicella zoster virus infection

204487 (ZOSTER-059 PRI) Statistical Analysis Plan Amendment 3

11. LIST OF FINAL REPORT TABLES, LISTINGS AND FIGURES

The TFL TOC provides the list of tables/listings and figures to be included in the study report.

The following group names will be used in the TFLs, in line with the T-domains:

Group order in tables	Group label in tables	Group definition for footnote	
1	Co-Ad	Dose 1: Prevenar 13 + HZ/su, Dose 2: HZ/su	
2	Control	Dose 1: Prevenar 13, Dose 2: HZ/su, Dose 3: HZ/su	

The following sub-groups will be used in the TFL, in line with the T-domains:

Table 6 Group Definitions to be used for the sub-group analysis by age (Analysis will be included in the clinical report)

Sub-group order in tables	Sub-group label in tables	Sub-group definition for footnote
1	50-59YOA	Subjects aged 50-59 years
2	60-69YOA	Subjects aged 60-69 years
3	≥70YOA	Subjects aged 70 years and over

YOA = Year of age

Please note that for table presentation in the sub-group analysis, the sequence maintained has to be each treatment group within each age sub-group.

12. ANNEX 1 STANDARD DATA DERIVATION RULE AND STATISTICAL METHODS

12.1. Standard data derivation

12.1.1. Dose number

The study dose number is defined in reference to the number of study visits at which vaccination occurred. More specifically dose 1 refers to all vaccines administered at the first vaccination visit while dose 2 corresponds to all vaccinations administered at the second vaccination visit even if this is the first time a product is administered to the subject.

Associated dose: the associated dose for an event (AE, medication, vaccination) is the most recent study dose given before an event. In case the event takes place on the day a study dose is given, the associated dose will be that of the study dose, even if the event actually took place before vaccination. For instance, if an adverse event begins on the day of the study vaccination but prior to administration of the vaccine, it will be assigned to this dose. In case a study dose is not administered and an event occurs after the

204487 (ZOSTER-059 PRI) Statistical Analysis Plan Amendment 3

subsequent study dose (e.g. 2nd study dose), the associated dose of the event will be study dose associated to the subsequent study dose (e.g. dose 2).

The number of doses for a product is the number of times the product was administered to a subject.

The incidence per dose is the number of visits with vaccine administered at which an event was reported among all visits with vaccine administered.

12.1.2. Immunogenicity

- For a given subject and given immunogenicity measurement, missing or nonevaluable measurements will not be replaced. Therefore, an analysis will exclude subjects with missing or non-evaluable measurements.
- A seronegative subject is a subject whose antibodies concentration/titer is below the cut-off value (cut-off value is defined by the laboratory prior to the analysis).
- A seropositive subject is a subject whose antibodies concentration/titer is greater than or equal to the assay cut-off value.
- The seropositivity rate is defined as the percentage of seropositive subjects.
- The VRR for anti-gE is defined as the percentage of subjects who have at least:
 - a 4-fold increase in the anti-gE antibodies concentration as compared to the prevaccination anti-gE antibodies concentration, for subjects who are seropositive at baseline, or,
 - a 4-fold increase in the anti-gE antibodies concentration as compared to the anti-gE antibodies cut-off value for seropositivity, for subjects who are seronegative at baseline.
- The GMC calculations for anti-gE antibody concentration are performed by taking the anti-log of the mean of the log base 10 concentration transformations. Antibody concentrations below the cut-off of the assay will be given an arbitrary value equal to half the cut-off for the purpose of GMC/GMT calculation.
- All CI computed will be two-sided 95% CI.

204487 (ZOSTER-059 PRI) Statistical Analysis Plan Amendment 3

• Updated LLOQ and ULOQ values for the MOPA assay are described below for each of the 13 pneumococcal serotypes:

Pneumococcal serotype	Method	Unit	LLOQ1	ULOQ	Laboratory
Streptococcus pneumoniae Serotype 01/37 Brugmann Hospital Ab			14	3504	
Streptococcus pneumoniae Serotype 03/1 Statens Serum Institut Ab			11	2822	
Streptococcus pneumoniae Serotype 04/2656 Brugmann Hospital Ab			40	18042	
Streptococcus pneumoniae Serotype 05 Ambrose- Statens Serum Institut Ab			15	13304	
Streptococcus pneumoniae Serotype 06A Centers for Disease Control Ab			45	15305	
Streptococcus pneumoniae Serotype 06B/DS2212/94 Centers for Disease Control Ab			29	20806	University of
Streptococcus pneumoniae Serotype 07F/46 Brugmann Hospital Ab	MOPA	1/ dilution	28	59809	University of Alabama at
Streptococcus pneumoniae Serotype 09V/112 161/95 Statens Serum Institut Ab			39	28095	Birmingham
Streptococcus pneumoniae Serotype 14/58 Brugmann Hospital Ab			16	47856	
Streptococcus pneumoniae Serotype 18C/4593/40 Statens Serum Institut Ab			40	13318	
Streptococcus pneumoniae Serotype 19A/DB18 Kansanterveyslaitos Folkhalsoinstitutet Ab			13	34881	
Streptococcus pneumoniae Serotype 19F/2737 Brugmann Hospital Ab			33	29352	
Streptococcus pneumoniae Serotype 23F Mac- Statens Serum Institut Ab			40	10662	

¹LLOQ corresponds to serotype-specific assay cut-off value.

• The Geometric Mean Titres (GMTs) calculations for pneumococcal serotypes are performed by taking the anti-log of the mean of the log base 10 titre transformations. For GMT calculation for pneumococcal serotypes, antibody titres below the LLOQ of the assay will be given an arbitrary value of half the cut-off for GMT calculation. Antibody titres above the ULOQ of the assay will be given the value of ULOQ for GMT calculation.

12.1.3. Safety

For a given subject and the analysis of solicited adverse event during the 7 day follow-up period after vaccination, missing or non-evaluable measurements will not be replaced. Therefore, the analysis of the solicited adverse events based on the ES will include only vaccinated subjects with documented safety data (i.e., symptom screen completed). More specifically the following rules will be used:

- Subjects who documented the absence of a solicited adverse event after one dose will be considered not having that adverse event after that dose.
- Subjects who documented the presence of a solicited adverse event and fully or
 partially recorded daily measurement over the solicited period will be included in the
 summaries at that dose and classified according to their maximum observed daily
 recording over the solicited period.

204487 (ZOSTER-059 PRI) Statistical Analysis Plan Amendment 3

- Subjects who documented the presence of a solicited adverse event after one dose
 without having recorded any daily measurement will be assigned to the lowest
 intensity category at that dose (i.e., 38°C for fever or grade 1 for other adverse
 events). The subject will only be presented in the subject with adverse event
 experienced and not in specific grade information.
- Doses without adverse event sheets documented will be excluded.

For analysis of unsolicited AEs, such as SAEs or adverse events by MedDRA Primary SOC and PTs term, and for the analysis of concomitant medications, all vaccinated subjects will be considered. Subjects who did not report the event or the concomitant medication will be considered as subjects without the event or the concomitant medication respectively.

Associated dose: The associated dose for an event (e.g., AE, medication, vaccination,...) is the study dose given before an event. In case the event takes place on a day a study dose is given, the associated dose will be that of the study dose even if the event actually took place before. For instance, for a conc. medication started on the day of study dose 2 but before dose 2 administrations, the associated dose will be dose 2

The way the percentage of subjects will be derived will depend on the event analysed (see the following table for details). As a result, the denominator (N) will differ from one table to another.

Event	N used for deriving %	Terminology used in the tables for N
Concomitant	All vaccinated subjects	Number of subjects with at least one
medication		administered dose
Solicited local	All vaccinated subjects with at least one	For each dose and overall/subject:
adverse event	solicited local adverse event	N= number of subjects with at least one
	documented as either present or absent	documented dose
		For overall/dose:
		N= number of documented doses
Solicited general	All vaccinated subjects with at least one	For each dose and overall/subject:
adverse event	solicited general adverse event	N= number of subjects with at least one
	documented as either present or absent	documented dose
		For overall/dose:
		N= number of documented doses
Unsolicited adverse	All vaccinated subjects	Number of subjects with at least one
event from day 0 to		administered dose
day X		
SAE	All vaccinated subjects	Number of subjects with at least one
		administered dose

- The maximum intensity of local injection site redness and swelling will be scored at GSK Biologicals as follows:
 - 0 : <20 mm
 - 1 : > 20 mm to < 50 mm diameter
 - 2: > 50 mm to \leq 100 mm diameter
 - 3 : > 100 mm diameter

204487 (ZOSTER-059 PRI) Statistical Analysis Plan Amendment 3

Fever is defined as temperature $\geq 38.0 \text{ C} / 100.4 \text{ F}$ for oral, axillary, tympanic or rectal route. The preferred route for recording temperature in this study will be oral. For the analysis, temperatures will be coded as follows:

Grade	Temperature (oral, axillary, tympanic or rectal route)	
0	< 38°C	
1	≥ 38°C - ≤ 38.5°C	
2	> 38.5°C - ≤ 39°C	
3	> 39°C	

• Conversion of temperature to °C -

The following conversion rule is used for the conversion of temperature to °C

Temperature in °Celsius = ((Temperature in °Fahrenheit -32) *5)/9

The result is rounded to 1 decimal digit.

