5.7.13. Recording of AEs, SAEs, pregnancies and pIMDs

- Refer to Section 8.3 for procedures for the investigator to record AEs, SAEs, pregnancies and pIMDs. Refer to Section 8.4 for guidelines and how to report SAE, pregnancy and pIMD reports to GSK Biologicals.
- The subjects will be instructed to contact the investigator immediately should they manifest any signs or symptoms they perceive as serious.
- At each vaccination visit, diary cards will be provided to the subject. The subject will be instructed to measure and record the oral body temperature, and any solicited local/general AEs (i.e. on the day of vaccination and during the next 6 days) or any unsolicited AEs (i.e. on the day of vaccination and during the next 29 days occurring after vaccination). The subject will be instructed to return the completed diary card to the investigator at the next study visit.
- Collect and verify completed diary cards during discussion with the subject (at Visit Month 1 and Visit Month 3 in Co-Ad group and at Visit Month 1, Visit Month 4 and Visit Month 5 in Control group).
- Any unreturned diary cards will be sought from the subject through telephone call(s) or any other convenient method.
- The investigator will transcribe the collected information into the eCRF in English.

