10.5.1. Handling of missing data

For the analysis of solicited symptoms, missing or non-evaluable measurements will not be imputed. Therefore, the analysis of the solicited symptoms based on the TVC will include only subjects/doses with documented safety data (i.e. symptom screen completed).

For the analysis of unsolicited AEs/SAEs/pIMDs/concomitant medication, all vaccinated subjects will be considered and subjects who did not report an event will be considered as subjects without an event.

For a given subject and a given immunogenicity measurement, missing or non-evaluable measurements will not be replaced. Therefore, a subject will be excluded from an analysis if all measurements are missing or non-evaluable.

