95%CI= Exact 95% confidence interval; LL = lower limit, UL = upper limit

204487 (ZOSTER-059 PRI) Statistical Analysis Plan Amendment 3

Template 18 Incidence of solicited general adverse events reported during the 7day (Days 1-7) post-vaccination period following each dose and overall <Exposed Set>

					<each gr<="" th="">		</each>		
							5 % CI
Dose	Adverse event	Туре	N	n	%	LL	UL
Dose 1	Fatigue	All					
		Grade 3					
		Related					
		Grade 3*Related					
		Medical advice					
	Gastrointestinal symptoms	All					
		Grade 3					
		Related					
		Grade 3*Related					
		Medical advice					
	Headache	All					
		Grade 3					
		Related					
		Grade 3*Related					
		Medical advice					
	Myalgia	All					
		Grade 3					
		Related					
		Grade 3*Related					
		Medical advice					
	Shivering	All					
		Grade 3					
		Related					
		Grade 3*Related					
		Medical advice					
	Fever (Oral) (°C)	All (≥38.0)					
		>38.0					
		>38.5					
		>39.0					
		>39.5					
		>40.0					
		Related					
		>39.0*Related					
		Medical advice					
Dose 2							
Dose 3							
Overall/Dose							
Overall/Subject							
	/enar 13+ H7/su Dose 2: H7/su						

Co-Ad = Dose 1: Prevenar 13+ HZ/su, Dose 2: HZ/su

Control = Dose 1: Prevenar 13, Dose 2: HZ/su, Dose 3: HZ/su

For each dose: N = number of subjects with the corresponding documented dose; n/% = number/percentage of subjects reporting the adverse event at least once following the corresponding dose

For Overall/dose: N = number of documented dose; n/% = number/percentage of doses followed by at least one type of adverse event

For Overall/subject: N = number of subjects with at least one documented dose; n/% = number/percentage of subjects reporting the type of adverse event at least once

95%CI= Exact 95% confidence interval; LL = lower limit, UL = upper limit

204487 (ZOSTER-059 PRI) Statistical Analysis Plan Amendment 3

Template 19 Summary of temperature value by half degree increment taken by different routes reported during the 7-day (Days 1-7) postvaccination following each dose < Exposed Set>

						С	o-Ad				Co	ntrol	
							95	% CI				95	% CI
Dose	Symptom	Route	Type	N	n	%	LL	UL	N	n	%	LL	UL
Dose 1	Temperature (°C)	Oral	≥35.0										
			>35.5										
			>36.0										
			>36.5										
			>37.0										
			>37.5										
			>38.0										
			>38.5										
			>39.0										
			>39.5										
			>40.0										
		Axillary	≥35.0										
		,	>35.5										
			>36.0										

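### The solicited-symptom denominators keep subjects who left that symptom blank, so a blank in effect counts as no event despite the plan's no-replacement rule

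*SAP*

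**What the plan says.** SAP Amendment 3, section 12.1.3 (Safety), sets the rules for solicited events. For the 7-day period, "missing or non-evaluable measurements will not be replaced", and the analysis takes only vaccinated subjects with "documented safety data (i.e., symptom screen completed". Absence comes from a recorded absence: "Subjects who documented the absence of a solicited adverse event after one dose will be considered not having that adverse event after that dose". The one stated exclusion works on whole doses: "Doses without adverse event sheets documented will be excluded". Protocol section 10.5.1 takes the same line: "For the analysis of solicited symptoms, missing or non-evaluable measurements will not be imputed".

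The denominator table in 12.1.3 then sets N for solicited local events as all vaccinated subjects with at least one solicited local event "documented as either present or absent". The row for general events is worded the same way. Templates 17, 18, 26 and 27, which report each symptom by dose, carry the footnote "N = number of subjects with the corresponding documented dose".

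For unsolicited events, both documents state a different convention outright: a vaccinated subject who did not report the event is treated as not having had it.

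**The concern.** The text of 12.1.3 works symptom by symptom, while the denominator works by class of symptom (local or general) or by dose. A subject who recorded fatigue but left temperature blank meets the class test for general events and so enters N for fever. With nothing recorded for fever, that subject cannot enter the numerator. The percentage treats the blank as no fever, although the plan says missing values are not replaced.

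Occurrence of each solicited event is the first-listed secondary endpoint (SAP 4.2), and section 6.4.1 asks for the percentage with each individual symptom and an exact 95% CI. If blanks occur, those percentages are not rates among subjects who supplied the information, and the intervals credit the estimate with subjects who contributed nothing to it.

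**Working it through.** **Does any rule cover a blank symptom?** Section 12.1.3 has four rules for solicited events: documented absence; documented presence with full or partial daily records; documented presence with no daily record; and exclusion of doses with no sheet. A symptom left blank on a sheet where another symptom of the same class is documented falls under none of them. The denominator table decides the matter by keeping that subject in N. Section 12.1.3 says that N differs between tables, but nothing makes it differ between symptom rows.

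**Local events at Co-Ad Dose 1.** Section 12.1.1 defines a dose as all vaccines given at one visit, and Template 17 has separate rows for HZ/su and Prevenar13. As worded, a subject who documented one injection site is in N for both products.

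**Would the gap be visible?** Template 15 measures compliance as doses with screens returned, so a blank item on a returned screen would not show.

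**Size.** The plan states no solicited-event rate and no item-level missingness, so there is no figure to reproduce. Inputs:

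- N = 456, the planned number per group (Protocol 5.2.2.2.1), used only as an illustrative denominator.
- b = subjects with the symptom blank. Assumption: 0% to 10% of N.
- p = rate among subjects who documented the symptom. Assumption: 10% to 80%.

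Rate under the SAP = n/N. Symptom-specific rate = n/(N − b). If blanks are unrelated to the event, n is about p(N − b), so the SAP rate is about p(1 − b/N). Counts are rounded to whole subjects.

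| Blank share (b) | p | n | n/N | n/(N − b) | Gap, points |
|---|---|---|---|---|---|
| 0% (0) | 50% | 228 | 50.0% | 50.0% | 0.00 |
| 1% (5) | 50% | 226 | 49.6% | 50.1% | 0.55 |
| 5% (23) | 10% | 43 | 9.4% | 9.9% | 0.50 |
| 5% (23) | 50% | 216 | 47.4% | 49.9% | 2.52 |
| 5% (23) | 80% | 346 | 75.9% | 79.9% | 4.03 |
| 10% (46) | 10% | 41 | 9.0% | 10.0% | 1.01 |
| 10% (46) | 50% | 205 | 45.0% | 50.0% | 5.04 |
| 10% (46) | 80% | 328 | 71.9% | 80.0% | 8.07 |

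Over these ranges the gap runs from 0 to about 8.1 points.

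**Precision.** For a given rate, the binomial standard error goes as 1/√N. With 46 of 456 blank, √(410/456) = 0.948, so the interval would be about 5% too narrow.

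**If blanks are related to the event.** Suppose the true rate is 50%, 10% are blank, and every blank is a subject with nothing to report. All 228 events are documented, so n/N = 228/456 = 50.0%, which is right, and n/(N − b) = 228/410 = 55.6%, which is too high. The SAP rate is below the symptom-specific rate whenever b and n are above zero; whether it is below the truth depends on why items are blank.

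**The case against.** The strongest reply is that a completed symptom screen may mean every item answered, in which case the effect is zero. Protocol 5.7.13 points that way: cards are collected and verified in discussion with the subject, and the investigator transcribes them. The eCRF is not part of the documents, so blanks cannot be shown to occur. This stands as a limit on size. It does not remove the conflict, because the at-least-one test in the denominator table sets a lower bar than a fully answered screen and would be unnecessary if every item had to be answered.

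It can also be said that no sentence scores a blank as absent, and that SAP section 13 calls the template footnotes illustrative. Both are true. But the denominator table is in the body of the SAP, and it produces that result without saying so.

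A reader might infer two stronger things. One is that the reported rates are understated as a matter of fact. That needs blanks to exist and to be unrelated to the event, and the documents establish neither. The other is that the arms are biased differently, because Control cards are collected "at Visit Month 1, Visit Month 4 and Visit Month 5 in Control group". The card for Control's first HZ/su dose thus waits until Month 4 (49–83 days after the dose), against Month 1 (30–42 days) for Co-Ad's. But symptoms are recorded daily on Days 1–7 in both arms (Protocol Tables 6 and 7), and nothing links the time of collection to blank items. The templates also tabulate by dose number, which sets Co-Ad Dose 1 beside Control Dose 1, and both of those cards are collected at Month 1.

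**Conclusion.** The inconsistency is real and worth correcting. The no-replacement and documented-absence rules do not fit a denominator set by class of symptom or by dose, and the contrast with the explicit convention for unsolicited events suggests that scoring blanks as absent was not intended.

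The consequence is conditional. If item-level blanks occur, each individual-symptom rate is below the rate among subjects who documented that symptom, by the factor (1 − blank share) when blanks are unrelated to the event, and the exact CI uses too large an N. The size cannot be computed from the documents and may be zero.

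The any-local, any-general and any-AE rows are little affected, since the at-least-one N suits them. Solicited safety is descriptive, and SAP section 7 rests the trial's conclusion on the co-primary immunogenicity criteria alone, so no success criterion is touched.

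**What to change.** In the 12.1.3 denominator table and the footnotes of Templates 17, 18, 26 and 27, define N for each symptom and dose (and each product for local events) as subjects with that symptom documented as present or absent after that dose. Carry the same rule into the overall and across-dose rows. For fever, say what counts as documented, for example at least one temperature recorded or fever marked as absent.

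Keep the at-least-one denominator for the any-local, any-general and any-AE rows. Report the number of blank items per symptom and group, so that a reader can judge whether the choice of denominator matters, including the case where blanks mean nothing to report. If the eCRF does not accept a blank item, one sentence saying so would settle the question of size.

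The cost is a change of SAP wording and of how N is programmed, with no new data. The small downside is that denominators will vary between symptom rows.
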